5.3 Statistical Methods for Safety Analyses

The analysis set for all safety analyses is defined in Section 2.1. Baseline will be defined as the last measurement prior to exposure to study lenses. For biomicroscopy data, baseline will be defined as Visit 2 for Period 1 and Visit 5 for Period 2. Safety variables will be summarized descriptively.

5.3.1 Adverse Events

The applicable definition of an AE is in the study protocol. All AEs occurring from when a subject signs informed consent to the time of their study exit will be accounted for in the reporting.

Presentation of AEs will be separated into pre-treatment AEs, between-treatment AEs, and treatment-emergent AEs as defined below:

- Pre-treatment: an event that occurs after signing informed consent but prior to exposure to study lenses
- Between-treatment: an event that occurs one day after last exposure to Period 1 study lenses but prior to exposure to Period 2 study lenses
- Treatment-emergent: an event that occurs from exposure to Period 1 study lenses until subject exits from the study, excluding those classified as between-treatment

The following tables and supportive listings will be provided:

- Incidence of All Ocular Treatment-Emergent Adverse Events
- Incidence of All Nonocular Treatment-Emergent Adverse Events
- Listing of All Ocular Treatment-Emergent Adverse Events
- Listing of All Nonocular Treatment-Emergent Adverse Events
- Listing of All Ocular Pre-Treatment Adverse Events
- Listing of All Nonocular Pre-Treatment Adverse Events
- Listing of All Ocular Between-Treatment Adverse Events
- Listing of All Nonocular Between-Treatment Adverse Events

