7.3 Procedures for Recording and Reporting

AEs are collected from the time of informed consent. Any preexisting medical conditions or signs/symptoms present in a subject prior to the start of the study (i.e., before informed consent is signed) are not considered AEs in the study and should be recorded in the Medical History section of the eCRF.

In addition, temporary lens awareness or visual changes during the fitting process are not considered AEs if the investigator assesses that the symptom(s) can reasonably resolve within the anticipated adaptation period.

For each recorded event, the ADEs and SAEs documentation must include: date of occurrence, severity, treatment (if applicable), outcome, and assessments of the seriousness and causality. In addition, the investigator must document all device deficiencies reported or observed with test and comparator products on the Device Deficiency eCRF. The site must submit all available information on ADEs, SAEs, and device deficiencies to the study sponsor immediately as follows:

- ADEs or SAEs are documented on the *Serious Adverse Event and Adverse Device Effect* eCRF within 24 hours of the investigator's or site's awareness.
- Device deficiencies are documented on the *Device Deficiency* eCRF within 24 hours of the investigator's or site's awareness.
- A printed copy of the completed *Serious Adverse Event and Adverse Device Effect* and/or *Device Deficiency* eCRF must be included with product returns.
- Additional relevant information after initial reporting must be entered into the eCRF as soon as the data become available.
- Document all relevant information from Discharge Summary, Autopsy Report, Certificate of Death, etc., if applicable, in narrative section of the *Serious Adverse Event and Adverse Device Effect* eCRF.

Note: Should the EDC system become nonoperational, the site must complete the appropriate paper *Serious Adverse Event and Adverse Device Effect* and/or *Device Deficiency* Form. The completed form is emailed to the study sponsor at [contact] according to the timelines outlined above; however, the reported information must be entered into the EDC system once it becomes operational.

Any AEs and device deficiencies for nonstudy marketed devices/products (i.e., CLEAR CARE Cleaning & Disinfecting Solution) will be considered and processed as spontaneous

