7.5 Follow-Up of Subjects with Adverse Events

The investigator is responsible for adequate and safe medical care of subjects during the study and for ensuring that appropriate medical care and relevant follow-up procedures are maintained after the study.

The investigator should provide the study sponsor with any new safety information (which includes new AEs and changes to previously reported AEs) that may affect the safety evaluation of the device. For AEs that are unresolved/ongoing at time of subject discontinuation or exit from study, any additional information received at follow-up should be documented in the eCRFs up to study completion (i.e., database lock).

Any additional data received up to 1 month after subject discontinuation or exit must be documented and available upon the study sponsor's request. All complaints received after this time period will be considered and processed as spontaneous and should be communicated to the medical device's manufacturer as per local requirements.

The investigator should also report complaints on non-Alcon products directly to the manufacturer as per the manufacturer's instructions or local regulatory requirements.

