2 ANALYSIS SETS

2.1 Safety Analysis Set

Safety analyses will be conducted using the safety analysis set on a treatment-emergent basis. As such, the safety analysis set will include all subjects/eyes exposed to any study lenses evaluated in this study, [REDACTED]

For treatment-emergent safety analyses, subjects/eyes will be categorized under the actual study lenses exposed in the corresponding lens sequence.

Adverse events occurring from the time of informed consent but prior to first exposure to study lenses will be summarized in subject listings.

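### SAP 5.3.1 has no worsening rule, so an AE that starts in a washout and worsens on the next lens can miss that lens's incidence table

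*SAP*

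**What the plan says.** SAP 5.3.1 defines three classes of AE, each by timing alone. The treatment-emergent class takes in "an event that occurs from exposure to Period 1 study lenses until subject exits from the study, excluding those classified as between-treatment". The pre-treatment class runs from consent up to the first wear of any study lens. The remaining class belongs to the second washout, and the SAP words it as "an event that occurs one day after last exposure to Period 1 study lenses but prior to exposure to Period 2 study lenses".

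Two incidence tables are planned, ocular ("Incidence of All Ocular Treatment-Emergent Adverse Events") and its nonocular counterpart. Pre-treatment and between-treatment AEs get listings only.

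On attribution to a lens, the visible part of SAP 2.1 says that "subjects/eyes will be categorized under the actual study lenses exposed in the corresponding lens sequence". Some text in that section is redacted.

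On recording, Protocol 7.5 asks the investigator to pass on "new AEs and changes to previously reported AEs", so it names a change to a known AE separately from a new one. Protocol 7.3 asks for later information on a reported device-related or serious event to be added to the eCRF.

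**The concern.** A lens that aggravates an existing eye problem has had an effect that its AE incidence should show. Under SAP 5.3.1 the deciding fact is when the event occurred, and nothing is said about what it did afterwards. If a site updates the existing record when the AE worsens, the record keeps its first date and its first class. A washout AE that becomes severe on the next lens then enters neither lens's incidence.

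The SAP already applies the missing principle to slit-lamp signs. SAP 5.3 resets the biomicroscopy baseline at Visit 2 and Visit 5, and SAP 5.3.2 tabulates increases of two or more grades. Worsening from a period-specific baseline therefore counts for biomicroscopy but not for AEs.

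**Working it through.** **Step 1. Apply the definitions to three cases, each entered once and then updated.**

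| Onset | Worsens on | Class under SAP 5.3.1 | In an incidence table? |
|---|---|---|---|
| First washout | Lens 1 | Pre-treatment | No, listing only |
| Second washout | Lens 2 | Between-treatment, expressly excluded from treatment-emergent | No, listing only |
| Period 1 | Lens 2 | Treatment-emergent | Yes, but no visible rule says the worsening counts under Lens 2 |

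If the site instead enters the worsening as a new AE, that AE occurs during lens wear and is counted in all three cases. The result thus depends on a recording convention that the visible text does not state.

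**Step 2. Weight of one subject.** The plan has 60 subjects to complete and about 68 to enroll. 1/60 = 1.67 points and 1/68 = 1.47 points of a lens's incidence.

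**Step 3. How many events could be involved.** The documents give no AE rate, duration or worsening share, so there is no planned figure to reproduce. From the documents: 68 subjects, washouts of 2 to 4 days, periods of 14 to 16 days (two visit intervals of 7 to 8 days). Assumed: 0.05, 0.10 or 0.20 AEs per subject per 28 days at a constant rate; exponential durations with mean m of 4, 7 or 14 days; washout and period lengths uniform over their windows; 25% of ongoing AEs worsen on the lens.

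Simulated number of earlier-onset AEs still ongoing when a lens is first worn, per trial (4,000 trials):

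| AE rate | m = 4 | m = 7 | m = 14 |
|---|---|---|---|
| 0.05 | 0.73 | 1.08 | 1.58 |
| 0.10 | 1.47 | 2.15 | 3.10 |
| 0.20 | 2.89 | 4.32 | 6.31 |

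Multiplied by 0.25:

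| AE rate | m = 4 | m = 7 | m = 14 |
|---|---|---|---|
| 0.05 | 0.18 | 0.27 | 0.40 |
| 0.10 | 0.37 | 0.54 | 0.78 |
| 0.20 | 0.72 | 1.08 | 1.58 |

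Seven of the nine values are below one event. The Poisson chance of at least one, 1 − exp(−x), runs from 17% (x = 0.18) to 79% (x = 1.58).

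**Step 4. Separate events missing from both tables from events only unassigned.** Let λ = 68 × rate / 28 be onsets per day in the trial, W the washout length and P the period length. The expected numbers ongoing at first wear are:

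- from the two washouts: 2λm(1 − E[exp(−W/m)])
- from Period 1 into Period 2: λm · E[exp(−W/m)] · (1 − E[exp(−P/m)])

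with E[exp(−W/m)] = (m/2)(exp(−2/m) − exp(−4/m)) and E[exp(−P/m)] = (m/2)(exp(−14/m) − exp(−16/m)).

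At rate 0.05, λ = 0.1214:

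| m | E[exp(−W/m)] | E[exp(−P/m)] | Washout onset | Period 1 onset | Sum |
|---|---|---|---|---|---|
| 4 | 0.477 | 0.024 | 0.51 | 0.23 | 0.73 |
| 7 | 0.654 | 0.118 | 0.59 | 0.49 | 1.08 |
| 14 | 0.808 | 0.343 | 0.65 | 0.90 | 1.56 |

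The sums agree with the simulation to within its random error. Rate 0.20 multiplies each entry by four. Taking 25%, washout-onset AEs that worsen, which are the ones that can miss both tables, number 0.13 (0.25 × 0.51) to 0.65 (0.25 × 4 × 0.65) per trial. The rest of the 0.2 to 1.6 are Period 1 AEs, which are counted once and lack only a rule for the second lens.

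**The case against.** The strongest reply is that the loss is conditional and partly guarded against. Protocol 7.2 makes a clinically relevant adverse change in a measured parameter or questionnaire response reportable as an AE. Protocol 5.2 requires an AE form for relevant signs or symptoms that suggest sensitivity or intolerance to a study lens. That would reach many cases of irritation that becomes severe and ends participation. Protocol 7.1 names ocular events to be reported whenever they occur. This stands as a limit on size. None of these sections says that a worsening needs a new record with its own date, so they do not settle the class.

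It is also true that the events stay visible. They appear in listings, Protocol 6.8 identifies serious and significant nonserious AEs and those leading to discontinuation, SAP section 3 lists discontinued subjects, and slit-lamp worsening is tabulated. In a study of this size they could be found case by case. A listing is still not an incidence.

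Three stronger readings are tempting, and the documents do not support them:

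- *Every worsened AE is lost.* This holds only for washout-onset AEs that are updated and not re-entered.
- *A Period 1 AE that worsens on Lens 2 is charged only to Lens 1.* That is the natural reading, but it is an inference. The visible text is silent, SAP 2.1 is partly redacted, and the AE footnote to the visit schedule is not shown.
- *Protocol 7.3 bars aggravation of a pre-consent condition from being an AE.* It says that conditions present before consent "are not considered AEs in the study and should be recorded in the Medical History section of the eCRF". It does not say that their later worsening is not an AE.

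**Conclusion.** The point holds and is minor. As written, SAP 5.3.1 keeps a washout-onset AE that is updated as it worsens out of the next lens's incidence table, and no visible rule assigns the worsening of a Period 1 AE to the second lens. Whether a worsening is counted depends on how each site records it.

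The firm figure is 1.5 to 1.7 points of a lens's incidence per subject. The 0.2 to 1.6 events per trial rest wholly on the assumed rate, duration, constant onset and 25% worsening share. The totals equal 20%, 30% and 43% of the treatment-emergent count for m of 4, 7 and 14 days, so a quarter is about 5% to 11%. A reader might take that as a large bias, but it usually stands for less than one event. The study is descriptive, with no safety hypotheses and no success criteria, and 1:1 allocation to sequence spreads the effect over both lenses on average. That balance does not restore an undercount common to both.

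**What to change.** In SAP 5.3.1, add a clause along these lines: *An AE with earlier onset (pre-treatment, between-treatment or Period 1) that increases in severity or becomes serious after first exposure to a period's lens is also treatment-emergent, and is counted under the lens worn when it worsened.* Limit the between-treatment exclusion to events that do not worsen in Period 2.

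In the eCRF instructions, tell sites to record a worsening with its own date, so that the clause can be applied from the data.

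Optionally, state in Protocol 7.3 how worsening of a pre-consent condition is to be recorded. This is a clarification and the main fix does not depend on it.

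The cost is a few sentences and one recording instruction, with no added visits, procedures or subjects. The small downside is that a few more events may be counted and one illness may appear under both lenses; a footnote to the incidence tables can say so.

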5.3.2 Biomicroscopy Findings

The following tables and supportive listings will be provided:

- Frequency and Percentage for Biomicroscopy Findings by Visit
- Incidence of Increased Severity by 2 or More Grades in Biomicroscopy Findings
- Listing of Subjects With Other Biomicroscopy Findings
- Listing of Subjects With Conjunctival Compression/Indentation or Chemosis
- Listing of Subjects With Increased Severity by 2 or More Grades in Biomicroscopy Findings
- Listing of Subjects with Infiltrates

5.3.3 Device Deficiencies

The following tables and supportive listings will be provided:

- Frequency of Treatment-Emergent Device Deficiencies
- Listing of Treatment-Emergent Device Deficiencies
- Listing of Device Deficiencies Prior To Treatment Exposure

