1.2 Study Description

Key components of the study are summarized in Table 1-1.

Table 1-1 **Study Description Summary**

Study Design	Prospective, randomized, bilateral crossover, double-masked
Study Population	Volunteer subjects aged 18 or over who are habitual spherical soft contact lens wearers (excluding current/previous ACUVUE OASYS® 2 Week with HYDRACLEAR® PLUS (AOHP) habitual lens wearers and daily disposable lens wearers), have at least 3 months of contact lens wearing experience, and who wear their habitual lenses at least 5 days per week and at least 8 hours per day. [REDACTED] [REDACTED] [REDACTED] [REDACTED] [REDACTED] Target to complete: 60 Planned to enroll: ~68
Number of Sites	~5 US
Test Product(s)	Alcon serafilcon A contact lenses (serafilcon A; LID022821)
Comparator Product(s)	ACUVUE OASYS® 2 Week with HYDRACLEAR® PLUS (AOHP; senofilcon A)
Planned Duration of Exposure	~28 days total duration (test and comparator) plus wash-out: Test Product: ~14 days Comparator Product: ~14 days
Visits	Prescreening (optional) Visit 1 – Screening/Baseline Visit 2 – Dispense Lens 1 [2 (at least 48 hours) - 4 days after Visit 1*]

	
Visit 3 – Week 1 Follow-up Lens 1 [7 -0/+1 days after Visit 2] Visit 4 – Week 2 Follow-up Lens 1 [7 -0/+1 days after Visit 3] Visit 5 – Dispense Lens 2 [2 (at least 48 hours) - 4 days after Visit 4*] Visit 6 – Week 1 Follow-up Lens 2 [7 -0/+1 days after Visit 5] Visit 7 – Week 2 Follow-up Lens 2/Exit [7 -0/+1 days after Visit 6]
 
* Washout period with habitual spectacles only after Visit 1 and after Visit 4

--	--

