Dispense study lenses			X	X		X	X				(X)
VA w/ study lenses (OD, OS, logMAR distance)			X	X	X	X	X	X	(X)		(X)

Procedure/ Assessment	Pre-screening	Lens 1 (Period 1)				Lens 2 (Period 2)				Early Exit	Unscheduled Visit
		Visit 1 Screening / Baseline	Visit 2 Dispense Lens 1 [2 (at least 48 hours) - 4 days after Visit 1 (Washout period with habitual spectacles only after Visit 1)]	Visit 3 Week 1 Follow-up Lens 1 [7 -0/+ 1 days after Visit 2]	Visit 4 Week 2 Follow-up Lens 1 [7 -0/+ 1 days after Visit 3)]	Visit 5 Dispense Lens 2 [2 (at least 48 hours) - 4 days after Visit 4 (Washout period with habitual spectacles only after Visit 4)]	Visit 6 Week 1 Follow-up Lens 2 [7 -0/+ 1 days after Visit 5]	Visit 7 Week 2 Follow-up Lens 2 /Exit [7 -0/+ 1 days after Visit 6)]			

Procedure/ Assessment	Pre-screening	Lens 1 (Period 1)				Lens 2 (Period 2)				Early Exit	Unscheduled Visit
		Visit 1 Screening / Baseline	Visit 2 Dispense Lens 1 [2 (at least 48 hours) - 4 days after Visit 1 (Washout period with habitual spectacles only after	Visit 3 Week 1 Follow-up Lens 1 [7 -0/+ 1 days after Visit 2]	Visit 4 Week 2 Follow-up Lens 1 [7 -0/+ 1 days after Visit 3)]	Visit 5 Dispense Lens 2 [2 (at least 48 hours) - 4 days after Visit 4 (Washout period with habitual spectacles only after Visit 4)]	Visit 6 Week 1 Follow-up Lens 2 [7 -0/+ 1 days after Visit 5]	Visit 7 Week 2 Follow-up Lens 2 /Exit [7 -0/+ 1 days after Visit 6]			

Procedure/ Assessment	Pre-screening	Lens 1 (Period 1)				Lens 2 (Period 2)				Early Exit	Unscheduled Visit
		Visit 1 Screening / Baseline	Visit 2 Dispense Lens 1 [2 (at least 48 hours) - 4 days after Visit 1 (Washout period with habitual spectacles only after Visit 1)]	Visit 3 Week 1 Follow-up Lens 1 [7 -0/+ 1 days after Visit 2]	Visit 4 Week 2 Follow-up Lens 1 [7 -0/+ 1 days after Visit 3)]	Visit 5 Dispense Lens 2 [2 (at least 48 hours) - 4 days after Visit 4 (Washout period with habitual spectacles only after Visit 4)]	Visit 6 Week 1 Follow-up Lens 2 [7 -0/+ 1 days after Visit 5]	Visit 7 Week 2 Follow-up Lens 2 /Exit [7 -0/+ 1 days after Visit 6)]			
Unplanned lens replacement with reason			(X)	(X)	(X)	(X)	(X)			(X)	
AEs ^a		X	X	X	X	X	X	X	X	X	
Device deficiencies		X	X	X	X	X	X	X	X	X	
Exit Form								X	X		

(X) assessment performed as necessary e.g. reduction of VA by 2 lines or more with investigational product (IP)

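### Does a lens defect found at Visit 5, before the second lens type is worn, drop out of every device deficiency output?

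*SAP*

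**What the plan says.** SAP 5.3.3 plans three outputs for device deficiencies: the table "Frequency of Treatment-Emergent Device Deficiencies", a listing of the same records, and "Listing of Device Deficiencies Prior To Treatment Exposure". Protocol 6.8 plans the same pair of listings and adds that every deficiency category will be tabulated. Neither section says where one class ends and the other begins.

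The SAP is fuller for adverse events. SAP 5.3.1 has three classes. Its treatment-emergent class runs from first wear in Period 1 "until subject exits from the study, excluding those classified as between-treatment", and the interval between periods has its own outputs, such as "Listing of All Ocular Between-Treatment Adverse Events". No such listing exists for deficiencies.

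Two other places in the SAP mark a point of exposure. SAP 2.1 says that adverse events "prior to first exposure to study lenses will be summarized in subject listings". SAP 5.3 says: "For biomicroscopy data, baseline will be defined as Visit 2 for Period 1 and Visit 5 for Period 2".

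**The concern.** Visit 5 is when each subject first receives the second lens type. It follows the interval that SAP 1.2 describes as "Washout period with habitual spectacles only after Visit 1 and after Visit 4", so no study lens should have been worn for at least 48 hours. Table 10-1 schedules both "Dispense study lenses" and the collection of deficiencies at that visit. Protocol 7.1 counts lenses torn in the pack and packaging faults as deficiencies, so a reportable defect can be found before anything touches the eye.

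If a programmer carried the adverse event classes over to SAP 5.3.3, such a record would be neither before treatment nor treatment-emergent. It would appear in none of the three outputs. A programmer who cut at first exposure to any study lens would count it in the table, and one who worked period by period would only list it. Device deficiencies are one of the three safety endpoints, so the completeness and reproducibility of that part of the report seemed to be at stake.

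**Working it through.** **Step 1: where Visit 5 falls under the adverse event classes.** Inputs from SAP 1.2: Visit 3 is 7 or 8 days after Visit 2, Visit 4 is 7 or 8 days after Visit 3, and Visit 5 is 2 to 4 days after Visit 4. Take day 0 as Visit 2 and assume that the first lens type is last worn on the day of Visit 4.

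- Day of Visit 5 = (7 or 8) + (7 or 8) + (2, 3 or 4), which gives 2 × 2 × 3 = 12 combinations.
- Earliest: 7 + 7 + 2 = day 16. Latest: 8 + 8 + 4 = day 20.
- Gap since the first lens type was last worn: 2 to 4 days, always more than the one day at which the between-treatment class begins.

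On those terms, a defect seen before any Period 2 lens is inserted is between-treatment in all 12 combinations and enters 0 of the 3 outputs. If one eye is fitted before the second lens is opened, a defect in that second lens comes after Period 2 exposure has begun for the subject, and the result no longer holds automatically.

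**Step 2: whether those terms govern deficiencies.**

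| Place | What it covers | Where it would put a Visit 5 defect if applied |
|---|---|---|
| SAP 5.3.1 | Adverse events | No output |
| SAP 2.1 | Adverse events before first exposure | After first exposure, so treatment-emergent |
| SAP 5.3 | Biomicroscopy baseline | Before Period 2 exposure, so the pre-exposure listing |
| SAP 5.3.3, protocol 6.8 | Device deficiencies | Not spelled out; two classes, before and after |

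Only the last row is about deficiencies. The other three are rules for other data, so they are not competing rules for this endpoint. Before exposure and treatment-emergent form a natural complementary pair, and under either way of drawing the line (per period or once per study) every record lands in one of the planned outputs.

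**Step 3: how many lens openings are involved.** Assume that all 68 planned subjects reach Visit 5, wear lenses in both eyes, and that packs are opened when dispensed.

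- Visit 2: 68 × 2 = 136. Visit 5: 68 × 2 = 136.
- Week 1 dispensing on Table 10-1 (both periods): 68 × 2 × 2 = 272. Total 136 + 136 + 272 = 544; Visit 5 share 136/544 = 25%.
- Week 1 dispensing on the protocol 4.1 replacement periods (test lens only): 68 × 2 = 136. Total 136 + 136 + 136 = 408; Visit 5 share 136/408 = 33%.
- If only the 60 targeted completers reach Visit 5: 60 × 2 = 120 openings there.
- By lens, with 34 subjects per sequence: 34 × 2 = 68 comparator and 34 × 2 = 68 test, so neither lens is favoured.

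These figures cap how many openings could give rise to such a record. They say nothing about how many would.

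**The case for a change.** The best case for a change is that setting SAP 5.3.1 aside does not supply a definition. It leaves the class undefined, and the SAP's own wording about exposure points in different directions, so two careful programmers could each defend a different placement. Attribution to a lens is also open: SAP 2.1 groups subjects and eyes by the lens they were actually exposed to, while a Period 2 lens rejected before insertion was never worn. The mismatch may well have arisen because the SAP added a between-treatment class for adverse events and left deficiencies on the protocol's two classes. A clarifying sentence would cost little.

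Much of this stands as description. The labels are undefined, and a sentence would do no harm. It does not show that a stated rule produces a wrong result. Losing the record requires importing the one definition that creates a gap into a section that never cites it, and then not noticing that a form in the database appears in no output. Attribution has a simple answer, since protocol 6.8 reports deficiencies as recorded on the Device Deficiency Form and the defective lens is known from that record. A third listing would itself depart from the two that protocol 6.8 specifies. A between-treatment class borrowed from SAP 5.3.1 would also leave open how to order a defect and a first insertion on the same day.

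**Conclusion.** No change to the plan follows. SAP 5.3.3 and protocol 6.8 leave two timing labels undefined for deficiencies, which is a gap in detail that analysts can be expected to fill sensibly. The statement that a Visit 5 defect fits no output is true on one reading only, and that reading is not the one the deficiency sections invite.

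The possible effect is limited to which descriptive output shows a small number of records, possibly none. Protocol 7.3 requires sites to document every deficiency for both lenses within 24 hours, so no data are lost. There are no hypotheses and no success criteria, and under 1:1 randomization the affected openings divide evenly between the lenses.

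This rests on three assumptions: visits kept within their windows, packs opened at dispensing, and no contrary definition in the redacted parts of SAP 2.1 and protocol 6.2.1. Those sections are blacked out close to where treatment-emergent is introduced, so it cannot be confirmed that SAP 5.3.1 holds the SAP's only definition.
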